3.3 Study Procedures and Flowchart

Study subjects or subjects' parent/legal representative will be informed by study staff of the possibility for enrollment in the PMS study while attending a visit at the participating clinic or hospital, for the purpose of vaccination with MenACWY-CRM according to the local routine clinical care.

Informed consent must be obtained from the subject, or where applicable, the subject's parent(s) or legally acceptable representative(s) prior to the performance of any study related procedures.

At the visit, for each subject, data will be collected on the respective source document and then recorded on the appropriate section of the CRF.

Visit 1 - Day 1

- Written informed consent from the subject or subject's parents/legal representative, will be obtained.
- It will be checked whether subject conforms to inclusion and exclusion criteria (see section 4.0).
- Medical history will be collected and recorded on the Medical History CRF.
- A physical exam/assessment, including height, weight and body temperature (preferably axillary) will be performed and results recorded before vaccination.
- Demographic data will be collected and recorded.
- The study vaccine will be administered intramuscularly in the deltoid, preferably of the non-dominant arm. If the investigator determines that the subject's health on the day of vaccination temporarily precludes vaccination, according to the indication reported in the vaccine leaflet, the visit may be rescheduled.
- The subject will be observed closely for at least 30 minutes in the clinic after vaccination, with appropriate medical treatment readily available in case of a rare anaphylactic reaction following the administration of vaccines. Any local or systemic reaction observed within 30 minutes post vaccination will be recorded in the Adverse Event CRF.
- All subjects, or, where applicable, the subject's parents/legal representative, will be dispensed a Diary Card with instructions on how to complete it:
 - Days 1-7: record all local (erythema, induration, pain) and systemic (chills, nausea, malaise, myalgia, arthralgia, headache, rash, fever) reactions, all other AEs and SAEs, and all medications used to treat them;
 - Days 8-29: record all medically attended AEs and SAEs and all medications used to treat them.

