Male				X ² -test or Exact test
Female				
Total				

Table 2.1.6 Summary of AE by Past diagnosis

Safety Set	No. subjects with AE n (%)	No. AEs n	Total n (%)	p-value
Yes				X ² -test or Exact test
No				
Total				

Table 2.1.7 Summary of AE by Temperature Location

Safety Set	No. subjects with AE n (%)	No. AEs n	Total n (%)	p-value
Axillary				X ² -test or Exact test
Oral				
Rectal				
Ear				
Total				

Table 2.1.8 Summary of AE by Administration Site

Safety Set	No. subjects with AE n (%)	No. AEs n	Total n (%)	p-value
Left Deltoid				X ² -test or Exact test
Right Deltoid				
Left Thigh (Infant only)				
Right Thigh (Infant only)				
Other				
Total				

Table 2.1.9 Summary of AE by Concomitant medication

Safety Set	No. subjects with AE n (%)	No. AEs n	Total n (%)	p-value
Yes				X ² -test or Exact test
No				
Total				

Table 2.1.10 Summary of AE by Kidney Disorder

Safety Set	No. subjects with AE n (%)	No. AEs n	Total n (%)	p-value
Yes				X ² -test or Exact test
No				
Total				

Table 2.1.11 Summary of AE by Liver disorder

Safety Set	No. subjects with AE n (%)	No. AEs n	Total n (%)	p-value
Yes				X ² -test or Exact test
No				
Total				

Table 2.1.12 Summary of AE by Pregnancy

Safety Set	No. subjects with AE n (%)	No. AEs n	Total n (%)	p-value
Yes				X ² -test or Exact test
No				
Total				

Table 2.1.13 Summary of AE by Number of previous MenACWY

Safety Set	No. subjects with AE n (%)	No. AEs n	Total n (%)	p-value
0				X ² -test or Exact test
1				
2				
3				
Total				

Table 2.1.14 Summary of AE by Study vaccination number

Safety Set	No. subjects with AE n (%)	No. AEs n	Total n (%)	p-value
1				

Safety Set	No. subjects with AE n (%)	No. AEs n	Total n (%)	p-value
2				X ² -test or Exact test
3				
4				
Total				

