
Medications: Any medications used to treat any solicited local and systemic reaction and unsolicited AE be collected.
	From Day 1 to Day 7

Medications: Any medications used to treat any medically attended AE or SAE will be collected.
	From Day 1 to study termination (Day 29/early termination)

	CONFIDENTIAL :	Last Update Date
	THIS DOCUMENT AND INFORMATION CONTAINED HEREIN IS PROPRIETARY TO COMPANY AND IS NOT TO BE DISCLOSED WITHOUT THE WRITTEN PERMISSION OF COMPANY.	20-APR-2018
STATISTICAL ANALYSIS PLAN(V6.0)		

3. Analysis Sets

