6.1 Baseline Characteristics

Descriptive statistics (mean, standard deviation, median, minimum and maximum) for baseline characteristics such as age, height and weight at enrollment will be calculated in the Safety set and Safety per Protocol set.

The following baseline characteristics will be reported:

< Subject Baseline Information >

- gender, age, ethnic origin, children group, weight, height, past diagnosis, kidney disorder, liver disorder, pre-Immunization temperature, temperature location, pregnancy

< Study Vaccine Information >

- vaccine site, number of previous Menveo, study vaccination number, concomitant medications

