6.2.1 Adverse Events by Baseline Characteristics

AE[†]s (as described below) will be reported (n %) for the following baseline characteristics in the safety set and safety per protocol set :

- Age group (2-23 months, 2-10, 11-18, 19-34, 35-55, 55-64)
- Children group (<18, ≥18)
- Gender (male, female)
- Past diagnosis (yes, no)

	CONFIDENTIAL :	Last Update Date
	THIS DOCUMENT AND INFORMATION CONTAINED HEREIN IS PROPRIETARY TO COMPANY AND IS NOT TO BE DISCLOSED WITHOUT THE WRITTEN PERMISSION OF COMPANY.	20-APR-2018
STATISTICAL ANALYSIS PLAN(V6.0)		

- Temperature location (axillary, oral, rectal, ear)
- Administration site (left deltoid, right deltoid, left thigh, right thigh, other)
- Concomitant medication (yes, no)
- Kidney disorder (yes, no)
- Liver disorder (yes, no)
- Pregnancy (yes, no)
- Number of previous Menveo (0, 1, 2, 3)
- Study vaccination number (1, 2, 3, 4)

The n(%) of AEs[†] and its 95% confidence interval will be calculated using the normal approximation and analyzed using χ^2 - test. If more than 20% of expected frequencies of the cell counts are less than 5, Fisher’s exact test will be used instead of the chi-square test.

† AE : AE includes solicited and unsolicited AE (DAY 1-7), medically attended AE (DAY 1-29) and SAE (DAY 1-29).

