7.2 Baseline Characteristics

- Mean and standard deviation (SD) or frequency and percentage by gender, age, ethnic origin, weight, height, past diagnosis, pre-Immunization temperature, temperature location, pregnancy
- Frequency and percentage by vaccine site, number of previous Menveo, study vaccination number, concomitant medications.

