7.4 Additional Analyses for DDS (Data Disclosure Shell)

- Frequency and percentage by Age group (2-23 months, 2-10, 11-18, 19-64)
- Frequency and percentage by study termination and reason not completed
- Incidence proportion and the number of Non-SAE
- The number of death resulting from AE (frequency and percentage)
- Incidence proportion and number according to the preferred terms of Non-SAE (frequency and percentage)

7.5 Additional Analyses for AE in the Local Product Label (Unsolicited AE Day 1-29)

- Preferred terms of Serious AE/ADR, unexpected AE/ADR will be presented respectively according to the proportion.

	CONFIDENTIAL :	Last Update Date
	THIS DOCUMENT AND INFORMATION CONTAINED HEREIN IS PROPRIETARY TO COMPANY AND IS NOT TO BE DISCLOSED WITHOUT THE WRITTEN PERMISSION OF COMPANY.	20-APR-2018
STATISTICAL ANALYSIS PLAN(V6.0)		

8. Notes

- Each statistical analysis will be carried out with SAS Software version 9.4 or more recent version.
- In the descriptive statistics, mean, SD, minimum, median, and maximum will be calculated for continuous variables, and frequency and percentage for categorical variables.
- Data including sign of inequality such as “ ≥ 20 ”, “ > 20 ” will be excluded from analysis.
- All test statistics will be the results of two-sided tests with the statistical significant level of 0.05.
- The followings shall be included only in re-examination report:
 - Analysis by type of concomitant medications
 - Item ② of paragraph 6.2.3
 - Estimation of 95% confidence interval for incidence proportion of AEs by background factors
 - Paragraph 6.3, 6.4

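### Concomitant medication is tested as a baseline factor for AEs, but the plan records only drugs given to treat an AE, so *yes* follows from the outcome

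*SAP*

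**What the plan says.** **What is analysed.** SAP V6.0 section 6.2.1 (Adverse Events by Baseline Characteristics) includes "Concomitant medication (yes, no") among its factors. For each factor it asks for n (%), a normal-approximation 95% CI and a chi-square test, replaced by Fisher's exact test when expected counts are small. Section 8 sets two-sided 0.05. The outcome is any solicited or unsolicited AE on Days 1-7, or any medically attended AE or SAE on Days 1-29. Section 6.1 gives the same variable a baseline label ("vaccine site, number of previous Menveo, study vaccination number, concomitant medications"), as does section 7.2 ("Frequency and percentage by vaccine site, number of previous Menveo, study vaccination number, concomitant medications"). Section 8 adds "Analysis by type of concomitant medications" to the re-examination report without saying what is compared. The latest table shell in the documents, in V4.0 Appendix 1 ("Table 2.1.9 Summary of AE by Concomitant medication"), has a p-value column.

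**What is collected.** The Safety Assessment Table in SAP section 2.4 has two medication rows. For Days 1-7: "Any medications used to treat any solicited local and systemic reaction and unsolicited AE be collected". For Day 1 to study termination: "Any medications used to treat any medically attended AE or SAE will be collected". The protocol carries the same restriction in the diary instructions of section 3.3 (for Days 8-29, "record all medically attended AEs and SAEs and all medications used to treat them"), in the Day 29 procedures, and in sections 5.3 and 5.5. Section 5.5 also states that medication taken before the study is not collected. The Times and Events Table marks concomitant medications at Day 1, but its footnote f refers back to the Safety Assessment Table.

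**The concern.** A baseline factor has to be fixed before the outcome can occur. Here every trigger in the SAP for recording a drug is itself a component of the AE outcome. A recorded *yes* therefore implies an AE. The implication runs one way only: an untreated AE stays in *no*.

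Two distortions follow. The *yes* group shows an AE proportion of about 100%, and its normal-approximation CI collapses to zero width. The *no* group has lost its treated AE cases, so its proportion is too low. The test then rejects almost always, even if medication has no influence on AE risk. A reader of the re-examination report could take the result as a drug-vaccine interaction, or take the *no* figure as a background rate. Neither reading would be valid.

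**Working it through.** The plan states no figure for this comparison, so there is none to reproduce. The structure comes from the documents and the rates are assumed.

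**Inputs**
- N = 3,000 + 600 = 3,600 evaluable (SAP section 2.2).
- Test: uncorrected chi-square, two-sided 0.05 (SAP sections 6.2.1 and 8).
- Assumed: proportion with any AE, p = 40% (range 20-60%); share of AE subjects given a drug for it, q = 15% (range 5-30%).

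**Table implied by the written rule.** Let a = Np be the subjects with an AE and y = qa those treated.

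| | AE | no AE | AE % |
|---|---|---|---|
| *yes* | y | 0 | 100 |
| *no* | a - y | N - a | 100(a - y)/(N - y) |

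With one empty cell the chi-square simplifies to N·y·(N - a) / [(N - y)·a].

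**Main case**
- a = 3,600 × 0.40 = 1,440 and y = 1,440 × 0.15 = 216.
- *yes*: 216/216 = 100%; CI half-width 1.96 × √(1 × 0/216) = 0.
- *no*: (1,440 - 216)/(3,600 - 216) = 1,224/3,384 = 36.2%; SE = √(0.3617 × 0.6383/3,384) = 0.00826; CI 34.6-37.8%, wholly below the assumed 40%.
- Chi-square = 3,600 × 216 × 2,160 / (3,384 × 1,440) = 344.7, p = 6e-77 (342.0 with continuity correction).

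**Over the assumed range**

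| p | q | *yes* (all with AE) | *no*, AE % | chi-square |
|---|---|---|---|---|
| 20% | 5% | 36 | 19.2 | 145 |
| 20% | 30% | 216 | 14.9 | 919 |
| 40% | 5% | 72 | 38.8 | 110 |
| 40% | 30% | 432 | 31.8 | 736 |
| 60% | 5% | 108 | 58.8 | 74 |
| 60% | 30% | 648 | 51.2 | 527 |

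In the infant cohort alone (N = 600, main-case rates) the comparison is 36/36 against 204/564, chi-square 57.4, p = 3e-14.

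**How often the test rejects.** Simulating the SAP's rule at N = 3,600 with p from 10% to 70% and q from 2% to 20%, it rejects in 99.5-100% of runs. With a genuine baseline factor unrelated to AEs (10% users, 30% with an AE), the same test rejects in 4.9%. At p = 30%, three treated subjects are enough for p < 0.05.

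**If *yes* also contains other drugs.** Suppose an unrelated drug is recorded in a share u of all subjects, independently of AEs, at main-case rates. Then *yes* with an AE = 1,440 × [1 - 0.85(1 - u)] and *yes* without = 2,160u.
- u = 10%: 338.4/554.4 = 61.0% against 36.2%, chi-square 121, p = 4e-28.
- u = 30%: 583.2/1,231.2 = 47.4% against 36.2%, chi-square 42, p = 8e-11.

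**If some treated events are not counted as AEs.** Section 6.2.2 grades small redness or induration as absent. If 10% of *yes* subjects had only such an event: 216/240 = 90% against 1,224/3,360 = 36.4%, chi-square 268.

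**The case against.** The strongest reply is that the CRF is not in the documents and the SAP does not say which field defines *yes*. Protocol section 3.3.1, item D, lists concomitant medications and vaccine therapy with no AE restriction and with its own indication and start-date fields. If sites recorded every drug, *yes* is a mixture and 100% is only one scenario. That stands as a limit on the size. It does not rescue the factor, because AE-treating drugs still count in *yes*; the u = 10% and u = 30% cases show the association persisting. Item D also contains no instruction to record drugs unrelated to an AE.

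Second, protocol section 3.3 (Day 29) and sections 5.3 and 5.5 refer to drugs for any AE. A drug for a non-serious, non-attended event on Days 8-29 would give *yes* without a counted AE. Read alone, those sections do not force exactly 100%. The SAP table and the diary instructions do restrict that period to medically attended AEs and SAEs. The protocol body available is version 1, but the amendment logs list no content change to 5.3 or 5.5, and the V6.0 SAP table carries the same rule.

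Third, the shell has no CI column. That is correct: section 8 places CIs by background factor in the re-examination report only. The zero-width interval would appear there, not in Table 2.1.9.

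Fourth, protocol section 7.1 makes all analyses descriptive, and no decision depends on this p-value. This limits the severity, but the SAP still prescribes a test and the result still goes to the regulator. The very small p-values merely restate the empty cell and carry no further evidence.

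**Conclusion.** The concern holds. As written, the factor is a consequence of the outcome, and the comparison in section 6.2.1 carries no information on whether concomitant drugs affect AE risk. The direction follows from the SAP's own collection table and does not depend on any assumed rate. The size does: 100% against 36.2% at 40% AE incidence and 15% treated, with chi-square 74 to 919 over the range examined, and a smaller but still spurious gap (47.4% against 36.2%) if unrelated drugs were recorded in 30% of subjects. The damage is confined to this subgroup comparison, the baseline label in 6.1 and 7.2, and the undefined analysis by drug type. The four safety endpoints and the overall AE incidence are untouched. It should be fixed before the re-examination report is produced.

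**What to change.** - **Section 6.2.1:** delete concomitant medication from the factor list, the CI and the test, and drop the matching table in each analysis set (2.1.9 and 2.2.9 in the V4.0 shells).
- **Sections 6.1 and 7.2:** take concomitant medications out of the baseline lists. Report instead a descriptive row, *Subjects with AEs treated with medication, n (%)*. Shells 1.1.7 and 1.2.7 can be relabelled for this.
- **Section 8:** define the analysis by type as a frequency listing of the drugs used, with no comparison of AE incidence by type.
- **If the regulator requires the factor:** define *yes* only from a drug or vaccine with a recorded start date before the injection (protocol 3.3.1, item D.3), where such records exist; otherwise state that the factor cannot be analysed. Since protocol section 5.5 says prior medication is not collected, the second outcome is likely. Date fields would also miss vaccines given the same day.

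The cost is wording in four SAP sections, one table removed and one relabelled per analysis set, and one fewer subgroup comparison for the regulator. No new data are needed.

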1.1 Safety Set

Table 1.1.1 Total subject

Safety Set	Total No. subjects (%)
Total	

Table 1.1.2 Demographic characteristics

1) (Administration start date)-(birth)+1

Safety Set		Total No. subjects (%)
Age(years) ¹⁾	No. subjects mean±std median min~max	
Age(months, years)	2-23 months	
	2-10 years	
	2-5 years	
	6-10 years	
	11-18 years	
	19-34 years	
	35-55 years	
	> 55 years	
	Total	
Children group(years)	< 18	
	≥ 18	
	Total	
Ethnic Origin	Asian	
	Black	

Safety Set		Total No. subjects (%)
	Caucasian Hispanic Other	
	Total	
Gender	Male Female	
	Total	
Weight(kg)	No. subjects mean±std median min~max	
Height(cm)	No. subjects mean±std median min~max	

Table 1.1.3 Past diagnosis

Safety Set	Total No. subjects (%)
Yes	
No	
Total	

Table 1.1.4 Pre-Immunization temperature

Safety Set	Total No. subjects (%)
No. subjects mean±std (°C) median min~max	

Table 1.1.5 Temperature Location

Safety Set	Total No. subjects (%)
Axillary	
Oral	
Rectal	
Ear	
Total	

Table 1.1.6 Administration Site

Safety Set	Total No. subjects (%)
Left Deltoid	
Right Deltoid	
Left Thigh (Infant only)	
Right Thigh (Infant only)	
Other	
Total	

Table 1.1.7 Concomitant medication

Safety Set	Total No. subjects (%)
Yes	
No	
Total	

Table 1.1.8 Kidney Disorder

Safety Set	Total No. subjects (%)
Yes	

No	
Total	

Table 1.1.9 Liver disorder

Safety Set	Total No. subjects (%)
Yes	
No	
Total	

Table 1.1.10 Pregnancy

Safety Set	Total No. subjects (%)
Yes	
No	
Total	

Table 1.1.11 Number of previous MenACWY

Safety Set	Total No. subjects (%)
0	
1	
2	
3	
Total	

Table 1.1.12 Study vaccination number

Safety Set	Total No. subjects (%)
1	
2	
3	
4	

Total	
-------	--

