2.3 Study population

2.3.1 Inclusion criteria

Individuals eligible for enrolment in this study are those:

	CONFIDENTIAL :	Last Update Date
	THIS DOCUMENT AND INFORMATION CONTAINED HEREIN IS PROPRIETARY TO COMPANY AND IS NOT TO BE DISCLOSED WITHOUT THE WRITTEN PERMISSION OF COMPANY.	20-APR-2018
STATISTICAL ANALYSIS PLAN(V6.0)		

1. Male and female subjects from 2 months to 55 years of the age at the time of vaccination (including all 55 years of age subjects, up to one day before their 56th year birthday), who are scheduled to receive vaccination with MenACWY-CRM conjugate vaccine, according to the local prescribing information and routine clinical practice
2. To whom the nature of the study has been described and the subject or subject's parent/legal representative has provided written informed consent (written assent from minors should be also obtained if required by the relevant IRB);
3. Whom the investigator believes that the subject can and will comply with the requirements of the protocol (e.g., completion of the Diary Card);
4. Who are in good health as determined by the outcome of medical history, physical assessment and clinical judgment of the investigator

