3.1 Safety Analysis Sets

Safety Set

All subjects who

- have signed an informed consent form, undergone screening procedure(s) and received a subject number,
- received a study vaccination,
- provided post vaccination safety data.

Safety per protocol set

All subjects in the safety Set with the exclusions of the following cases:

- (1) Subjects administered prior to the contract date.
- (2) Subjects who didn't receive MenACWY-CRM.
- (3) Follow-up failure: The subjects whose safety information cannot be identified due to follow-up loss.
- (4) Not applicable to the indication of study drug
[Indication]
- To prevent invasive meningococcal disease caused by Neisseria meningitides serogroups A, C, Y and W-135 in persons 2 months through 55 years of age.
- (5) Subjects who violate of Protocol: Those who do not meet one item at least of the inclusion/exclusion criteria.
[Inclusion criteria]
 - 1) Male and female subjects from 2 months to 55 years of the age at the time of Visit 1 (including all 55 years old subjects, up to one day before their 56th year birthday), who are scheduled to receive vaccination with MenACWY-CRM conjugate vaccine, according to the local prescribing information and routine clinical practice.
 - 2) To whom the nature of the study has been described and the subject or subject's parent/legal representative has provided written informed consent.
 - 3) Whom the investigator believes that the subject can and will comply with the requirements of the protocol.
 - 4) Who are in good health as determined by the outcome of medical history, physical

	CONFIDENTIAL :	Last Update Date
	THIS DOCUMENT AND INFORMATION CONTAINED HEREIN IS PROPRIETARY TO COMPANY AND IS NOT TO BE DISCLOSED WITHOUT THE WRITTEN PERMISSION OF COMPANY.	20-APR-2018
STATISTICAL ANALYSIS PLAN(V6.0)		

assessment and clinical judgment of the investigator.

[Exclusion criteria]

- 1) Contraindication, special warnings and/or precautions, as evaluated by the investigators, reported in the MenACWY-CRM conjugate vaccine Korean prescribing information
 - 2) Infants who were already enrolled in this trial for previous vaccination.
- (6) Subjects who prescribed off-label dosage:
- Vaccine schedule for children from 2 to 23 months of age :

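### SAP V6.0 compares AEs by pregnancy in the whole safety set, with no restriction to females and no not-applicable level, so the No group is not a like-for-like comparator

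*SAP*

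**What the plan says.** SAP V6.0, section 6.2.1, reports AEs "for the following baseline characteristics in the safety set and safety per protocol set", and one of those characteristics is "Pregnancy (yes, no". Each factor gets percentages, a 95% interval and a chi-square test, with Fisher's exact test as the fallback when more than a fifth of the expected counts are below 5. Section 8 adds: "All test statistics will be the results of two-sided tests with the statistical significant level of 0.05". The outcome is a composite of solicited and unsolicited AEs (Days 1 to 7) with medically attended and serious AEs (Days 1 to 29).

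The analysis sets are not limited by sex or age. Section 2.3.1 admits "Male and female subjects from 2 months to 55 years of the age at the time of vaccination", and section 3.1 requires consent, that the subject "received a study vaccination", and some safety data afterwards.

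The most recent table shells available are those of SAP V4.0, Appendix 1. "Table 1.1.10 Pregnancy" and "Table 2.1.12 Summary of AE by Pregnancy" (repeated as Tables 1.2.10 and 2.2.12 for the per-protocol set) have rows Yes, No and Total; the AE tables add a p-value cell. None has a not-applicable row or a females-only note. The same shells do mark a restricted row where one is meant, as in "Left Thigh (Infant only" for administration site. The V6.0 revision log records no change to the pregnancy factor.

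**The concern.** A comparison by pregnancy status is informative when pregnant women are set against women who could have been pregnant but were not. As written, the reference group is everyone else in the set. That group differs from pregnant women in sex and age. Its members under 6 years are also measured differently: SAP V6.0, sections 2.4 and 6.2.2, gives them another solicited checklist (tenderness, eating habits, sleepiness, irritability, vomiting and diarrhea in place of pain, chills, nausea, malaise, myalgia, arthralgia and headache). Redness and induration count as absent up to 9 mm below 6 years, but up to 24 mm from 6 years on.

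The SAP lists age group and gender as separate AE factors in the same section, so it allows that either may matter. If they do, the pregnancy table shows part of their effect under the label of pregnancy, with a p-value attached. Pregnancy is an item that the protocol singles out for rapid reporting (section 6.2.6), so a mislabelled difference could be over-read.

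**Working it through.** **Inputs from the plan (SAP V6.0, section 2.2).** 3,960 to be enrolled; 10% drop-out; about 3,000 evaluable subjects aged 2 to 55 years and 600 aged 2 to 23 months, so 3,600 in all.

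**The plan's own figure.** 3,600 × 1.10 = 3,960, which reproduces the stated enrolment. (Applied as a loss, 3,960 × 0.90 = 3,564, close to 3,600. Nothing below depends on the difference.)

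**Who cannot be pregnant.**
- Infants alone: 600 / 3,600 = 16.7%. This needs no assumption beyond the planned numbers.
- Infants plus males, with an assumed male share *m* of those aged 2 to 55: (600 + 3,000*m*) / 3,600.
  - *m* = 30%: 1,500 / 3,600 = 41.7%
  - *m* = 50%: 2,100 / 3,600 = 58.3%
  - *m* = 70%: 2,700 / 3,600 = 75.0%
- Pre-pubertal girls would add to each figure.

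**Apparent difference when pregnancy has no effect.** Let *f* be the share of non-pregnant women of child-bearing age in the No row, *pW* the AE proportion in women (pregnant or not) and *pO* that in everyone else. Then Yes minus No = (1 − *f*)(*pW* − *pO*). It is zero when *pW* = *pO*.

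**Simulation of the SAP's test rule.** 1,500 runs per scenario, two-sided 0.05, chi-square or Fisher by the 20% rule, no pregnancy effect. The documents do not give the number of pregnant subjects, the share of women of child-bearing age or the AE rates; all are assumed. Results with 20 pregnant subjects:

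| Women of child-bearing age, of 3,600 | *f* | AE rate, women / others | Apparent difference (points) | p < 0.05, No = everyone else | p < 0.05, No = women only |
|---|---|---|---|---|---|
| 15% | 520/3,580 = 14.5% | 50% / 40% | +8.5 | 12.4% | 4.6% |
| 15% | 14.5% | 50% / 30% | +17.1 | 40.2% | 4.5% |
| 25% | 880/3,580 = 24.6% | 50% / 40% | +7.5 | 11.4% | 4.1% |
| 25% | 24.6% | 50% / 30% | +15.1 | 28.1% | 5.1% |
| 40% | 1,420/3,580 = 39.7% | 50% / 40% | +6.0 | 8.1% | 5.3% |
| 40% | 39.7% | 50% / 30% | +12.1 | 24.7% | 4.5% |

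Check of the first row: (1 − 0.145) × (0.50 − 0.40) = 0.085.

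- Equal rates (50% in both): difference 0; rejection 3.5% to 4.5% with either comparator.
- Women lower (40% against 50%): difference −6.0 to −8.5 points; rejection 5.7% to 12.0%.
- 5 pregnant subjects: rejection 1% to 6% in all but one scenario, which gives 19%. Here the point estimate would mislead more than the p-value.
- 50 pregnant subjects: rejection up to 71% in the most extreme scenario.
- Women-only comparator: 1% to 6% in every scenario run.

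**The case against.** The strongest reply is that the SAP never says how males, children and infants are coded. It names two levels without assigning anyone to them. The shells are empty, and a Total row could count only subjects with a recorded answer. A CRF code for not applicable might already remove the others. The protocol's survey-item list (section 3.3.1) shows no pregnancy field, but that text belongs to the version for ages 11 to 55 and settles little. The shells available are V4.0; those of V6.0 may differ. All of this stands. A reader might infer that the plan places males and infants in the No row as a stated rule; the documents support only that this follows from applying the factor to the set as defined.

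Three further inferences go too far.
- That the comparison is confounded whatever the data show. Bias needs AE rates that differ between the pooled groups.
- That every male and child has a different checklist. The checklist and thresholds change only at 6 years, so males and children from 6 up are assessed as adult women are.
- That 58% is a property of the plan. It rests on an assumed half-male cohort; only 16.7% comes from the planned numbers.

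It is also fair to say that pregnancy safety does not rest on this table. Protocol section 6.2.6 requires pregnancies to be reported within 24 hours and, with the subject's agreement, followed to outcome. Section 7.6.3 provides AE listings by subject, and section 7.1 makes the analyses descriptive. How many pregnant subjects could enter either set depends partly on Korean prescribing information that is not in the file.

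These points limit the weight of the concern but do not remove it. If a not-applicable code exists, the SAP still needs a sentence saying so; if none exists, the comparator is wrong.

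**Conclusion.** The concern holds in a limited form. SAP V6.0 applies a two-level pregnancy factor to sets that include both sexes and all ages from 2 months, tests it, and neither restricts the denominator nor provides for subjects to whom the question does not apply. Followed literally, at least 16.7% of planned evaluable subjects sit in the No group although they cannot be pregnant; the full share depends on a sex split that is not given.

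Whether this distorts the result depends on the data. Under the assumed rates with 20 pregnant subjects, a gap of 10 to 20 points between women and others produces an apparent pregnancy difference of 6 to 17 points. These are illustrations, not forecasts.

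The consequence is small: one secondary table in each of the two sets. It is worth doing because it is cheap, and I would not rank it higher than that.

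**What to change.** In SAP section 6.2.1, limit the pregnancy factor to females within a child-bearing age range that the sponsor defines and writes into the plan. Apply the same condition to the AE-by-pregnancy tables (2.1.12 and 2.2.12 in the V4.0 shells; the numbering should be checked against the current shells). Show all other subjects in a separate not-applicable row outside the test, and state the denominator under each table. Set a minimum number of Yes subjects in advance; below it, list them individually and give no p-value. If the CRF already codes not applicable, one sentence saying how that code enters the table and its Total covers the not-applicable row, but the age range should still be stated.

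The cost is one subset condition and a footnote, with a smaller comparison group and hence a somewhat wider interval for the No row. No new data beyond sex and date of birth are needed, and no other table changes.
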